**(IRB) DATE: 4/28/2021**

# Brief Description

This is a drug study that will examine the physiochemical, PK/PD properties of ketamine infusion in postpartum lactating women and in women weaning from breastfeeding. Part 1 of this study will inform the safety of a future planned RCT studying the effect of ketamine vs. placebo administered during scheduled cesarean deliveries or in weaning women on pain, opioid use, side effects, breastfeeding, and other outcomes.

15 (goal of 6 complete subjects) mothers will be recruited who are planning to either exclusively bottle-feed or to withhold breastfeeding for the first 27 hours after birth (during infusion of 12 hours, plus 15 hours after infusion) or they will be women who have been breastfeeding and are planning on weaning their baby off of the breastmilk who will be at the CTRC clinic for 24 hours total. For the cesarean population, after cord clamping, an intravenous infusion of 0.1mg/kg/hr for 12 hours will be started without a loading dose. If the patient is a weaning woman, they will come into the CTRC clinic in Montefiore and will have infusion in the clinic for 12 hours. Side effects, vital signs, and pain/analgesia endpoints will be monitored and recorded. Breastmilk/colostrum, serum, and urine will be collected to measure ketamine and its metabolites. The results of part 1 will inform appropriate future trial in Part 2 (the Phase 2 RCT) to either exclude or permit breastfeeding mother-infant dyads.

# Study Aims

The objective of this study is to assess pharmacokinetics of ketamine in the women immediately post cesarean delivery or women weaning from breastfeeding. Study Hypotheses: Breastmilk secretion of ketamine is low and poses minimal risk for neonatal exposure

Study Aims:

Aim 1. Evaluate breastmilk secretion of ketamine and its metabolites during and after administration of intravenous ketamine infusion in women immediately post C-section or women weaning from breastfeeding

Aim 2. Quantify pharmacokinetics of ketamine infusion in lactating people

# Study Design

## 1. Total number of subjects to be enrolled at this site:

15 (maximum)

## 2. Describe and explain the study design:

Open-label lead-in evaluation of ketamine infusion and breastmilk secretion.

Part 1 is an open-label evaluation in women who are either exclusively bottle-feeding, planning to withhold breastfeeding for the first 27 hours after birth, or weaning women. The goal is to get 6 complete patients (target n=6). Analysis of breastmilk for ketamine and metabolites will be done on each patient. The results of this part will inform conducting an additional future open-label evaluation in breastfeeding mother-infant dyads for ketamine and metabolites.

The patients enrolled will undergo an open-label sub-anesthetic ketamine infusion at 0.1 mg/kg/hr to assess breastmilk secretion of ketamine and its metabolites. These women will be selected for their plan to exclusively bottle-feed or will be weaning; they will then receive the ketamine infusion in the trial dosing protocol, and provide blood and breastmilk samples during and after ketamine infusion, so that ketamine and its metabolites concentrations can be assessed.

Protocol for Study Drug/Intervention:

Ketamine - 0.1 mg/kg/hr IV infusion for 12 hours, not to exceed 8mg/hr.

Weight-based dosing will be done on term body weight (kg), minus 41% of ponderal increment (for the post-cesarean delivery cohort)

**3. Describe the primary and secondary study endpoints:**

Primary outcome: Breastmilk transfer: concentration of ketamine and its metabolites in breastmilk

**4. List the inclusion criteria:**

Cesarean Section Population:

Adult female patients (i.e., ≥18 years of age)

Able to provide informed consent

Cesarean Delivery, Scheduled or Non-Emergent (delivery within 15 minutes not necessary),

ASA PS 2 or 3, with or without E designation (delivery within 15 minutes not necessary)

Spinal anesthesia with intrathecal morphine

Multimodal postop analgesia with IV ketorolac, PO NSAID, and PO APAP

Women who do not plan to breastfeed or who want to temporarily withhold breastfeeding

Weaning Women Population:

Adult female patients (i.e., ≥18 years of age)

Able to provide informed consent

Female weaning baby off of breastfeeding

ASA PS 1, 2 or 3

Minimum production of 2mL/24 hours breast milk

**5. List the exclusion criteria:**

Cesarean Section Population:

Cesarean Delivery under General Anesthesia

Allergies to study medications

ASA PS 4 or 4E

ASA PS with E designation because delivery within 15 minutes required

ASA PS greater than 4 (moribund patients)

Contraindications to spinal anesthesia

Contraindications to NSAIDs (gastric bypass, etc.)

Contraindication to any other multimodal analgesia medicine

Psychiatric history (depression and anxiety NOT exclusion criteria)

Uncontrolled hyperthyroidism

Cardiac disease

Fever

Hypertension

Adverse occurrence during caesarean section such as hemorrhage, need for transfusion, hemodynamic instability

Placenta accreta or previa with large anticipated blood loss

History of hallucinations, alcohol or illicit substance use/abuse

History of chronic opioid therapy, or chronic pain (chronic pain - defined by any condition requiring consistent follow up with pain specialist or daily administration of pain medications that could augment sedative effects)

Pre-eclampsia with severe features

Weaning Women Population:  
Allergies to study medications  
ASA PS 4 or 4E  
ASA PS greater than 4 (moribund patients)  
Psychiatric history (depression and anxiety NOT exclusion criteria)  
Uncontrolled hyperthyroidism  
Cardiac disease  
Fever  
Hypertension  
History of hallucinations, alcohol or illicit substance use/abuse  
History of chronic opioid therapy, or chronic pain (chronic pain - defined by any condition requiring consistent follow up with pain specialist or daily administration of pain medications that could augment sedative effects)

## Methods

### 1. Provide a detailed description of all research activities

#### PART 1: LACTATION STUDY

Women who are planning not to breastfeed, who are willing to withhold breastfeeding for the first 27 hours after delivery, or women who are weaning off of breastfeeding will be approached.

After electronic screening and confirming eligibility, approach will be by the clinical anesthesia team or by the bedside nurse to assess the patient's interest in hearing more about the study. Interested patients will be provided with a full explanation of study-related goals and procedures. The informed consent document will be reviewed in its entirety with the potential subject. All questions will be answered to the subjects' satisfaction. The patient may decide on participation in the study at any time during or after the initial encounter, and the desire and duration for a potential waiting period will be at the full discretion of the subject. The study coordinator or investigators can be contacted after the subject makes a volitional decision to participate in the study. The physician investigators will obtain written informed consent. The consent will be provided by the patient themselves; no patients will be approached or recruited if they are unable to consent for themselves. Subjects will not be informed of the outcome of the study at this time except through routine reporting structures available to the public forum via ClinicalTrials.gov.

OR Women who are weaning from breastfeeding. We will use multiple recruitment methods which are shown in the recruitment section. The women will come into the CTRC in Montefiore to provide consent. Interested patients will be provided with a full explanation of study-related goals and procedures. The informed consent document will be reviewed in its entirety with the potential subject. All questions will be answered to the subjects' satisfaction. The patient may decide on participation in the study at any time during or after the initial encounter. The study coordinator or investigators can be contacted after the subject makes a volitional decision to participate in the study. The physician investigators will obtain written informed consent. The consent will be provided by the patient themselves; no patients will be approached or recruited if they are unable to consent for themselves. A study physician will perform a history and physical and confirm ASA inclusion criteria after consent on day of study drug administration. For this weaning population, a urine pregnancy test will be performed the morning of CTRC visit, after informed consent and prior to any study related procedures. A positive test allows

the PI or CO-Is to re-evaluate the participants eligibility for this study. Subjects will not be informed of the outcome of the study at this time except through routine reporting structures available to the public forum via ClinicalTrials.gov. The CTRC has 24/7 RN staff and it will be a 1:1 participant:RN ratio. All staff are trained on IV ketamine protocol. They will be discharged after 24 hours after the start of infusion or as seen medically fit by the discharging physician.

Ketamine will be delivered in an open-label fashion as follows: 0.1mg/kg/hr IV infusion after cord clamping or at CTRC at a scheduled time with the participant and clinic (maximum allowable dose 8mg/hr infusion rate), for a total duration of 12 hours. Pharmacokinetic studies will be performed on breastmilk, serum, and urine samples.

Blood samples: 3mL whole blood at each sample from an indwelling intravenous catheter or by fresh sample by 25g or smaller butterfly needle. Specimens will be placed on ice and stored within 24 hours at -20 to -80C until analysis. Timepoints for collection: 8-10hrs into study drug infusion; 12hrs into study drug infusion; after infusion end at the following times: 0.5hrs, 1hr, 2hr, 4hr, 8hr, 24hr.

Urine: Total volume of maternal urine will be taken in the first 24 hours post-operatively. Collected in hat placed in toilet bowl and filled into a urine container. Samples can be stored/stable at room temperature and transported to the laboratory for analysis within 24 hours.

Breastmilk: colostrum/breastmilk samples will be expressed by hand expression or pump to get total volume into "snappies (R)" specimen collection devices. Specimens will be placed on ice and stored within 24 hours at -20 to -80C until analysis. Timepoints for collection: T0-2hrs after infusion start (at first opportunity), during infusion (4hrs, 8hrs, 12hrs), after infusion ends (2hrs, 4hrs, 8hrs, 24hrs). Per study team communication, the post c-section and weaning samples will undergo the same analysis for assessment of metabolites, confirmed by Co-I, [name], overseeing the analysis.

Pain assessments: During 72 hour hospital stay, medical records will be reviewed to collect pain scores during the hospital stay

Side effect electronic diary: a novel app has been developed for the purpose of this study to make sound alerts to collect data at appropriate times. Assessments will be made within 1hr after start of study drug (at the earliest possible time); every 4 hr thereafter until 12 hr after study drug infusion start. Assessments will include: Dizziness, lightheadedness, bad dreams, nausea, vomiting, itchiness, hallucinations; LSD short form of Addiction Research Center Inventory, ARCI (psychomimetic effects).

Maternal vital signs (blood pressure, pulse rate, temperature, heart rate, respirations, and oxygen saturation, Richmond agitation-sedation scale (RASS) score) will be measured after infusion start: every 30 min for one hour, then q1hr for 3 hours, then every 4 hours per existing clinical standards for the 12-hour duration of infusion (existing clinical standards: blood pressure, pulse rate, temperature, heart rate, respirations, and oxygen saturation). If the infusion rate is increased by the anesthesiologist investigators, then vitals are rechecked within one hour. When the infusion is discontinued at 12 hours, vital signs monitoring will be hourly for the first 4 hours, then every 4 hours including blood pressure, pulse rate, temperature, heart rate, respirations, and oxygen saturations, until 24 hours after the start of the study drug infusion (= 12 hours after study drug discontinuation)

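### The side-effect diary and ARCI have no pre-infusion entry, so in this single-arm study symptoms already present cannot be separated from those that begin on ketamine

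*Protocol*

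**What the plan says.** In the Protocol (Methods, Part 1: Lactation Study), the electronic diary is timed as follows: "Assessments will be made within 1hr after start of study drug (at the earliest possible time", and then "every 4 hr thereafter until 12 hr after study drug infusion start". Its content is "Dizziness, lightheadedness, bad dreams, nausea, vomiting, itchiness, hallucinations; LSD short form of Addiction Research Center Inventory, ARCI (psychomimetic effects", that is, seven symptoms plus the ARCI short form. No pre-infusion entry of these items appears there or in the SAP.

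The design has no comparator. Study Design item 2 states: "The patients enrolled will undergo an open-label sub-anesthetic ketamine infusion at 0.1 mg/kg/hr". The size is given in the same item: "The goal is to get 6 complete patients (target n=6", with a maximum enrolment of 15 in item 1.

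The Brief Description lists tolerability among the data to be gathered: "Side effects, vital signs, and pain/analgesia endpoints will be monitored and recorded". It also says that Part 1 is to inform the safety of a later randomised trial, and side effects are among that trial's outcomes.

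The SAP has no section on the diary or the ARCI. Its descriptive statistics (section VIII) cover participant characteristics only.

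**The concern.** Without a control arm, a symptom can be linked to the drug only by showing that it was absent, or milder, before the drug was given. The schedule does not collect that information. A woman who arrives dizzy or nauseated and ticks the item at the first entry looks the same in the data as a woman whose dizziness or nausea began on ketamine. The ARCI has the same gap: a score during infusion can be reported, but a change cannot.

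What is at stake is the tolerability description carried forward to the randomised trial. In justifying the dose, the SAP (section II) refers to published infusions with few adverse events and no psychomimetic effects. The diary and ARCI are this study's own check on that expectation. With about 6 women, a single ambiguous report is a large fraction of the sample.

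**Working it through.** The documents state no figure on this point, so there is none to reproduce. The check is a reading of the schedule followed by an illustration of size.

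**Step 1. Is a baseline collected elsewhere?**
- Diary and ARCI: the first entry comes after infusion start.
- Vital signs and RASS: the Protocol's schedule for these also runs from infusion start.
- Weaning women: a physician takes a history and examines them on the dosing day (Methods). This may note some complaints, but it is not an entry of the same seven items or of the ARCI.
- Exclusion criteria: a history of hallucinations is excluded in both cohorts. Current nausea, dizziness or itch is not named.
- SAP: no baseline, no rule for attributing a symptom, and no diary analysis.

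Nothing in the plan replaces the missing entry.

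**Step 2. When do the entries fall?** Read literally, with the first entry at some time after 0 and no later than 1 hour, four-hour spacing up to 12 hours gives three entries. Examples are 0.5, 4.5 and 8.5 hours, or 1, 5 and 9 hours. All fall during the infusion. Only a nominal time-0 start would give four entries (0, 4, 8 and 12 hours), and the text does not describe one.

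**Step 3. How much does one case weigh?** With n = 6, one woman with a pre-existing symptom contributes 1/6 = 16.7% to the observed rate for that symptom.

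**Step 4. How likely is at least one such case?** Let p be the proportion of women who have a given symptom before infusion. The documents give no value, so p is an assumption. The formula is P(at least one of n) = 1 − (1 − p)^n.

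| Assumed p | n = 6 (target) | n = 15 (maximum) |
|---|---|---|
| 5% | 1 − 0.95^6 = 26% | 1 − 0.95^15 = 54% |
| 10% | 1 − 0.90^6 = 47% | 1 − 0.90^15 = 79% |
| 20% | 1 − 0.80^6 = 74% | 1 − 0.80^15 = 97% |

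At p = 2% and n = 6 the figure is 1 − 0.98^6 = 11%. These are chances that the symptom is present before dosing. For it to appear in the diary it must also persist to an entry; one that resolves before the first entry is never recorded.

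**The case against.** The strongest case on the other side is that little depends on the diary. The only listed endpoint is the concentration of ketamine and its metabolites in milk, and both aims concern milk transfer and pharmacokinetics. The decision named for Part 1 is whether breastfeeding pairs may enter the later trial. No rule in the documents uses the diary. This stands, and it limits the point to the tolerability description.

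A reader might infer that every pre-existing symptom will be counted as a ketamine effect, or that a planned estimate is biased upward by some number of false reports. The documents do not support that. They contain no attribution rule and no diary analysis. A total across all seven items would need one unsourced prevalence for symptoms as different as itch and hallucinations, and a history of hallucinations is an exclusion.

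A reader might also point to the eligibility wording, "Psychiatric history (depression and anxiety NOT exclusion criteria". None of the seven diary symptoms is a mood or anxiety item, and the documents show no link from that eligibility to the diary scores. It adds nothing here.

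The cesarean cohort supports the point only in part. The Protocol requires "Spinal anesthesia with intrathecal morphine", so other causes of symptoms are in place before ketamine starts, but they also act alongside the infusion. Itch or nausea that begins later would be new relative to a baseline and still not clearly due to ketamine. The SAP (section I) describes enrolment of weaning women only, and for them the morphine argument does not arise.

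Finally, there is no loading dose, so at a constant rate an entry within the first hour follows at most 1/12 (about 8%) of the 12-hour dose. That makes it an early, low-exposure reference. It is still taken on drug, and the plan does not designate it as a reference.

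**Conclusion.** The point holds in a limited form. Followed exactly, the plan yields symptom and ARCI data in which new and pre-existing effects cannot be told apart, and nothing in it prevents a pre-existing symptom from being reported as a side effect of ketamine. One such case among 6 women is an observed rate of 16.7%. The chance of at least one per symptom is 26% to 74% for an assumed prevalence of 5% to 20%, and lower if the true prevalence is lower. The size therefore rests on an assumption; the absence of a baseline rests on the text. For the ARCI, the supportable statement is that change from pre-dose cannot be estimated. The milk and pharmacokinetic results are unaffected. This is a cheap improvement, not a threat to the study's main result.

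**What to change.** **Data collection.** Add one app prompt before infusion start with the same seven items and the ARCI. This is straightforward at the weaning women's scheduled clinic visit. In cesarean women, place it at a feasible time before the infusion and record whether it came before or after the spinal. State that spinal anesthesia and intrathecal morphine remain confounders.

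**SAP.** Add a short paragraph saying that a symptom is reported as a side effect only if it is new or worse than the pre-infusion entry, and that the ARCI is reported as change from that entry.

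**Women already studied.** The SAP describes enrolment and sampling in the past tense, so the prompt may come too late for some or all of the women. For them, use the label 'symptoms recorded during infusion', state that no baseline was taken, and note any prior symptom documented in the dosing-day history and physical.

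**Cost.** One extra short questionnaire per woman and a few sentences in the SAP. In cesarean women the timing is harder to arrange and the benefit only partial.

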**Pharmacokinetics and Pharmacodynamic Data
Analysis Plan PART 1**

For

PROTOCOL: NCT04037085 and FDAAA801

STUDY TITLE:

**Ketamine to Improve Recovery After Cesarean
Delivery – Part 1**

(KINETIC)

VERSION 2.0

DOCUMENT DATE: 11/20/2022

I. Clinical Protocol

In a prospective, open label, observational design study, women who were weaning from breastfeeding were enrolled. Women were included if they were ≥ 18 years of age, able to provide informed consent, weaning from breastfeeding, ASA physical status 1, 2, or 3, and producing a minimum of 2mL breast milk every 24 hours. They were excluded if they were allergic to study medications, ASA physical status 4 or greater, had a history of psychiatric comorbidity, uncontrolled hyperthyroidism, cardiac disease, fever, hypertension, history of hallucinations, alcohol, or illicit substance abuse, were on chronic opioid therapy, or had chronic pain disorders.

II. Dose Administration

Subjects received a sub-anesthetic ketamine infusion at 0.1 mg/kg/hour for 12 hours (not to exceed 8mg/hr dose). The justification for intravenous administration for 12 hours of 0.1mg/kg/hr are based on pharmacokinetic studies in humans¹⁸⁻²⁰. Ketamine produces analgesia at plasma concentrations of 100-200ng/mL, which is a fraction of the plasma concentrations associated with general anesthetic doses (9000-25,000 ng/mL)^{18,19}. In longitudinal studies reporting ketamine infusions from 0.05 -1mg/kg/hr, significant reductions in pain scores with minimal adverse events and no psychomimetic effects were observed over infusions lasting up to 5 days, while the effect of ketamine on pain scores were notably varied according to infusion duration^{21,22}.

III. PK Sampling Schedule of Treatment Group

Blood samples (2-3mL each) were collected at 8, 10, 12, 12.5, 13, 14, 16, and 20 hours after ketamine infusion start. Plasma was obtained by centrifugation at room temperature and kept frozen until analysis. The entire human milk expressed was collected starting at the time of infusion initiation (t_0) and ending 12 hours after the infusion was stopped (t_{24}). Breastmilk was labeled by collection time and weighed to estimate the volume (1 gram = 1 mL) and stored at -80°C until analysis. Patient vital signs were monitored every hour and continuous pulse oximetry was done for 12 hours during the infusion and for 12 hours after infusion.

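### The side-effect diary and ARCI stop when the 12 h infusion stops, so no structured symptom assessment is scheduled for hours 12 to 24, although other observations continue

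*Protocol*

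**What the plan says.** **Diary schedule.** The Protocol (Methods, section 1, Part 1: Lactation Study) puts the first diary assessment within 1 h of the start of study drug and repeats it "every 4 hr thereafter until 12 hr after study drug infusion start". The items are "Dizziness, lightheadedness, bad dreams, nausea, vomiting, itchiness, hallucinations; LSD short form of Addiction Research Center Inventory, ARCI (psychomimetic effects").

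**Infusion.** The same section gives the infusion "for a total duration of 12 hours". SAP section II agrees: "Subjects received a sub-anesthetic ketamine infusion at 0.1 mg/kg/hour for 12 hours".

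**Observation after the infusion.** Vital signs are taken hourly for 4 h after the infusion stops and then 4-hourly, "until 24 hours after the start of the study drug infusion". The measures listed for that period are blood pressure, pulse and heart rate, temperature, respirations and oxygen saturation. The sedation score (RASS) appears only in the list that begins with the infusion. SAP section III likewise describes monitoring for 12 h after the infusion. Blood and milk sampling also continue after the infusion in both documents. Weaning women are normally discharged 24 h after infusion start, subject to the discharging physician's judgement. Cesarean women have a 72 h hospital stay, with pain scores taken from the medical record.

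**Purpose.** The Brief Description states: "Side effects, vital signs, and pain/analgesia endpoints will be monitored and recorded". It gives no time window. It also says that Part 1 will inform the safety of the later RCT, and it names side effects among that RCT's outcomes. The only endpoint listed under Study Design, item 3, is the concentration of ketamine and metabolites in breastmilk. The SAP has no side-effect schedule or analysis.

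**The concern.** The diary and the ARCI are the only structured symptom instruments in the plan, and both close at the moment the drug is stopped. The recovery period is left to whatever is volunteered or charted, although staff are still taking measurements and the app already exists.

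The bad-dreams item shows the mismatch most clearly. For weaning women, "a urine pregnancy test will be performed the morning of CTRC visit", and a 12 h infusion follows. With a morning start, the first night's sleep would mostly come after the last prompt.

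What is at stake is the description of maternal tolerability, not the milk or plasma results. A woman whose first symptom appears at, say, 15 h would enter the diary data as symptom-free. If the diary results were later quoted as covering the whole stay, they could understate how many women had each symptom.

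**Working it through.** **Inputs** (Protocol, Methods, section 1; SAP section II for the infusion length)
- First diary entry at time f, with 0 ≤ f ≤ 1 h after infusion start.
- Interval 4 h; last permitted time 12 h after start.
- Infusion ends at 12 h.
- Vital-sign monitoring ends at 24 h after start. The Protocol equates this with 12 h after discontinuation, and 24 − 12 = 12 reproduces it.

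**Diary times.** Under a strict 4 h interval, t = f + 4k for k = 0, 1, 2, …, with t ≤ 12.

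| First entry f (h) | Diary times (h) | Last entry (h) | Entries after 12 h | Last entry to 24 h |
|---|---|---|---|---|
| 0 | 0, 4, 8, 12 | 12 | 0 | 24 − 12 = 12 h |
| 0.25 | 0.25, 4.25, 8.25 | 8.25 | 0 | 24 − 8.25 = 15.75 h |
| 0.5 | 0.5, 4.5, 8.5 | 8.5 | 0 | 24 − 8.5 = 15.5 h |
| 1 | 1, 5, 9 | 9 | 0 | 24 − 9 = 15 h |

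If the later prompts are instead fixed at 4, 8 and 12 h from start, the last entry is at 12 h. The count after 12 h is 0 on every reading. The stretch to 24 h without an entry is 12 h at the least, and 15 to 15.75 h under the strict interval with a first entry at 0.25 to 1 h.

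**Other observations scheduled after 12 h and up to 24 h** (Protocol)
- Vital signs: 12 + (1, 2, 3, 4, 8, 12) = 13, 14, 15, 16, 20, 24 h, which is 6 checks.
- Blood: 12 + (0.5, 1, 2, 4, 8) = 12.5, 13, 14, 16, 20 h, which is 5 samples.
- Milk: 12 + (2, 4, 8) = 14, 16, 20 h, which is 3 samples.

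The further Protocol blood and milk samples at 24 h after infusion end fall at 36 h and are not counted here.

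**Is 'start' a slip for 'end'?** Unlikely. The vital-signs sentence in the same section distinguishes infusion start from discontinuation and converts one to the other.

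**Direction of any understatement.** Let p be the proportion of women with a given symptom in hours 0-12, and q the proportion of the remainder whose first occurrence is in hours 12-24. The 24 h cumulative incidence is p + (1 − p)q, which is never below p. The shortfall is (1 − p)q. The documents give no value for q, so its size cannot be stated.

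**Bad dreams.** No clock time is stated for the infusion. If it starts at 08:00 to 10:00 (an assumption), the diary closes at 20:00 to 22:00.

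**With the same 4-hourly diary run to 24 h.** f = 0 adds 16, 20 and 24 h; f = 1 adds 13, 17 and 21 h. Either way there are 3 post-infusion assessments instead of 0.

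**The case against.** Side effects are not an endpoint. Both aims are pharmacokinetic, the SAP plans no side-effect analysis, and the decision the Brief Description assigns to Part 1 is whether the RCT should exclude or permit breastfeeding dyads. With a target of 6 complete women, any side-effect proportion will be very imprecise: for 0 events in 6, the exact 95% upper limit is 1 − 0.025^(1/6) = 46%. A 0-12 h figure is also a valid during-infusion figure if labelled as such. All of this stands, and it limits the point to a minor one.

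Four stronger readings are tempting, and the documents do not support them.

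- *No symptom is recorded after 12 h.* What is absent is a scheduled diary or ARCI assessment. Chart pain scores continue, the general commitment to record side effects has no cut-off, and weaning women have one-to-one nursing, so spontaneous reports can be noted. The Protocol text also refers to a recruitment section that is not in the supplied copy, so adverse-event reporting could sit in a part not seen.
- *Part 1 passes a downward-biased side-effect rate to Part 2.* No such rate is formally handed over. The understatement arises only if a 0-12 h summary is read as covering 24 h, and it concerns cumulative incidence, not a rate per hour.
- *Every woman is still under observation.* The discharge clause allows a weaning woman to leave at another time.
- *The bad-dreams item cannot be answered.* The infusion is at a time agreed with the participant, and after a cesarean the 12 h window may run overnight. The mismatch is likely only for weaning women with a morning start.

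The objection leaves one thing untouched: the Protocol says side effects will be recorded and that Part 1 informs the RCT's safety, yet it schedules the symptom instruments for the infusion period only.

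**Conclusion.** The point holds as a minor, cheaply corrected gap. On any reading of the schedule, 0 diary or ARCI assessments fall in hours 12 to 24 after infusion start, alongside 6 vital-sign checks, 5 blood samples and 3 milk samples. Symptoms that first appear after the infusion are not systematically captured. For weaning women with a morning start, that probably includes bad dreams on the first night.

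A side-effect summary from Part 1 would cover the infusion period only, and could understate 24 h cumulative incidence if presented as covering the whole stay. By how much cannot be derived from the documents. The breastmilk endpoint and the pharmacokinetic conclusions are unaffected.

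The conclusion rests on the stated 12 h infusion, on 'start' meaning start in the diary sentence, and on there being no further symptom schedule in a part of the Protocol that was not supplied. It needs no assumption about how fast ketamine or its metabolites clear.

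**What to change.** **Remaining participants, if any, and Part 2.** Continue the same 4-hourly diary and ARCI prompts to 24 h after infusion start, for example at 16, 20 and 24 h, which are already vital-sign times. Ask about bad dreams on waking. State whether prompts run from infusion start or from the first entry, so that the last during-infusion entry does not drift to about 9 h. Report hours 0-12 and 12-24 separately.

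**Women already completed.** SAP version 2.0 (11/20/2022) describes enrolment and dosing of weaning women in the past tense, so extra prompts may no longer be possible for them. Label their side-effect results as '0-12 h, during infusion only', and give the actual time of the last entry.

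**Cost.** Three more prompts per woman in an existing app, during a stay that is normally already planned, with slightly more participant burden. A prompt during the night may need to be answered on waking. The change affects data collection only.
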